5.1 Inclusion and Exclusion Criteria

[figure not shown]
A broad inclusion criteria will be implemented to maximise the generalizability of our findings to PD populations and to facilitate study recruitment processes. These are that:

- Participants must be diagnosed with idiopathic Parkinson's Disease as defined by the UK PDS Brain Bank Criteria.
- Participants must report limitations to Activities of Daily Life (ADL, UPDRS subscale 2)
- Capacity to consent to the study
- Motivated to comply with the protocol
- An understanding of English sufficient to comply with the protocol
- Spouse/ carer willing to support the participant throughout the study

Exclusion Criteria:

- Diagnosis of induced Parkinson's or essential/dystonic tremor
- Premorbid psychiatric history (including affective disorder, psychosis or deliberate self-harm)
- Previous exposure to neurostimulation
- Inner ear pathology

Participant Test Schedule

Demographic data obtained from the participating institutions suggest that approximately 95% of the sample will be white British, 5% will be Asian, and a maximum of 1% will be black, Hispanic or from any

other ethnic or racial category. We will nevertheless continue to actively encourage all minority participants. We do not expect systematic differences in our results as a function of these factors. We point out that as this is a prospective study it is impossible to know in advance the exact proportion of eligible individuals who will be either female or from an ethnic minority.

5.2 Sample Size and Anticipated Effect

We will recruit individuals receiving PD care from the West or East Kent Neuro-rehabilitation, psychiatry, or allied services referred to study by the participating clinicians, Drs [name], and [name]. Using the attached flyer, we will also advertise for participants through the local branch of *Parkinson's UK* – participants from our previous pilot were successfully recruited through this means. The flyer will be distributed via the local branch's email list and also posted on their website.

For all study participants, a letter will be sent to their GP informing him/her of his/her patients' involvement.

As this is a pilot study aiming to establish potential effect sizes that in turn will power a subsequent, more definitive efficacy study, no formal sample size calculation has been performed, however, comparable intervention studies in the literature report statistically significant effects with sample sizes of this magnitude. We estimate a total of 40 participants will be recruited with the expectation that 32 patients and their carers will comply with both the intervention and follow-up.

6. Analysis

6.1 Plan and Statistical Considerations

Comparisons of scores on the behavioural measures in active and inactive (active, placebo) patients will be completed using formal parametric / nonparametric repeated measures tests. The results will be presented as group means (idiopathic cohort 1 and 2) with corresponding confidence intervals. Tests for assumptions will be conducted prior to analysis. For the electrophysiological measures, ANOVA will be used to compare elements of the ERP and more global aspects of the EEG across alternating blocks of active and sham stimulation.

If the active group is shown to be statistically superior to the placebo group then those in the placebo group will be offered the active treatment at the end of study. If there is evidence, as determined by the independent statistician, that a more prolonged treatment schedule may confer greater benefit then the placebo group will be offered the opportunity to receive 4 months of active treatment instead of the current 2. Regardless of whether 2 or 4 months of treatment is received, participants will repeat the assessment schedule that they completed during their earlier treatment phase, with the exception of EEG which given its time-consuming and burdensome nature will be dropped.

Adverse events, general concerns, dropouts and satisfaction will be presented as summary statistics for each group.

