2.4 Overview of the Design Study

To investigate the impact of CVS on PD, a diverse sample of 32 individuals diagnosed with Parkinson's disease from community and outpatient settings will be recruited and will have an equal chance of receiving active or placebo stimulation.

Participants will first complete an initial 4 week period of baseline assessment to quantify their deficits and isolate any improvements due to natural recovery. Next the participants will be divided; one group will proceed to a phase of active stimulation where they will undergo two twenty minute sessions of CVS each day. In order to control for placebo effects, the other group will receive sham stimulation where two 20 minute sessions of inactive stimulation will be given each day.

Participants will complete a battery of physiological and behavioural assessments at the end of every four weeks to monitor their progress on the core symptoms of interest. At the end of the study all participants will re-do the full baseline assessment to determine whether any of their symptoms have responded to the stimulation. Participants will undergo an EEG test at baseline and then at the end of the study protocol to assess changes at the neuro-physiological level. Additionally, all patients will be subject to a short video recording at baseline and at the end of the protocol to provide qualitative evidence to clinical audiences and potential funders post-study.

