4.2 Study Schedule

Potential participants will be identified by the key clinician. If the individual fulfils the entry criteria, he or she will be approached by the key clinician who will inform him or her of the aims and nature of the study. If the patient wishes to receive further information then the clinician will inform the team of key researchers, one of who will meet with them to discuss the study in detail and provide them with an information and consent sheet. The individual will have 24-48 hours to decide whether they would like to participate. Where a favourable view is given, the trial will commence approximately 1 week later at the same location. Upon study registration idiopathic participants will be randomly allocated to one of two treatment arms (see below) with a ratio of 1:1 (cohort 1: cohort 2) (see figure 2). Randomisation of condition allocation will be carried out using an online randomizer (www.randomizer.org).

All participants (n= 32) will complete an initial baseline assessment encompassing a range of behavioural and functional skills (executive function, memory, perception, pain, rehabilitative

progress). Physiological functioning will also be captured using EEG/ERP. This baseline will take place during the first week of enrolment and will then be repeated again during week 4 in order to measure the rate of any spontaneous recovery. We will also perform a video recording of mobility and any other assessments that show impairment at baseline and at the end of the study protocol for comparative reasons.

Cohort one (n=16) will then proceed to the active phase of stimulation whereby CVS will be administered by a staff member or carer (depending on their circumstance) twice a day for 20 minutes, 7 days a week. The CVS device will be pre-set to fluctuate between cold (17°) and warm temperatures (42°) thereby activating the vestibular system. Cohort two (n=16) will instead complete a placebo arm for the duration of the study protocol. During this phase the CVS device will be fitted as normal but the earpieces will remain unpowered, which does not activate the vestibular structures.

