Every four weeks, participants will be assessed on the core symptoms of interest. Their physiological activity will also be measured using EEG and heart rate variability (HRV), the latter of which can be simply recorded from one of the EEG electrodes. At the end of the treatment protocol the full baseline assessment will be repeated. 4 weeks post-intervention, the full baseline assessment will once again be repeated to assess carryover.

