4.4 Outcome Measures

Responsiveness to CVS will be measured using both behavioural and electrophysiological measures (detailed below). A variety of behavioural measures will be included to capture changes in the diverse array of symptoms patients present with. Physiological measures will also be used to monitor brain activity and more subtle changes in various physical functions and cognitive processes.

Behavioural: PD symptoms will be assessed using a neuropsychological test battery composed of standardised measures designed specifically for PD such as UPDRS and PDQ-39 and questionnaires that probe a variety of processes associated with motor skills and abilities

(inc. 2 Minute Walk, 10 Meter Walk and Timed Up and Go), memory (inc. MoCA); cognition (inc. Mini-Mental State Examination); mood (inc. HADS depression and anxiety); and fatigue/sleep disturbance (inc. Fatigue Severity Scale, Epworth Sleepiness Scale). More generalised benefits and activities of daily living will be assessed using measures such as the EQ5D3L and the Schwab and England Scale.

The behavioural measures will be administered at the two baseline assessments (week 1 and 4) and at the end of the treatment/placebo phases. A sample of the measures will also be administered during the interim monthly assessments and follow-up (weeks 8, 12 and 16).

ERP/EEG analysis: EEG abnormalities in PD are most prominently characterised by slower background activity (Neufeld, et al. 1998; Pin, et al. 1992) and changes of the alpha/theta index (Soikkeeli, et al. 1991). PD is also associated with a reduced and slower P300 response to auditory oddball stimuli. We will record these electrophysiological markers to help identify mechanism of effect and lend a degree of objectivity to the more subjective behavioural assessments. We will also analyse power within the main EEG frequency bands and record heart rate variability during the EEG sessions. EEG/ERP will be recorded at baseline and post-stimulation.

5. Study Participants

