***Caloric Vestibular Stimulation in
Parkinson's Disease***

NCT02703844

July 25, 2018

Statistical Analysis Plan (SAP)

Caloric Vestibular Stimulation to Treat Symptoms Associated with Parkinson's Disease

Prepared by: [name], Senior Statistician,
Centre for Health Service Studies
University of Kent

Final Version: 10 August 2017

Amended: 15 August 2018

Investigator: [name]

Sponsor: [name]

Signatures for approval of SAP

Prepared by Trial Statistician: [name] (University of Kent)

Signature:

Date:

Reviewed and approved by:

Principal Investigator: [name]

Signature:

Date:

1. Research question

Do repeated sessions of caloric vestibular stimulation (CVS) induce durable, potentially clinically meaningful improvements in the persistent and disabling motor and non-motor symptoms of Parkinson's disease?

2. Study design

This is a prospective single-blind randomised parallel group pilot study. The study was designed to recruit a diverse sample of 32 individuals diagnosed with idiopathic Parkinson's disease from community and outpatient settings. Participants will be individually randomised to active and placebo arms.

Diagnosis	Treatment (2 x 20 mins sessions per day for 8 weeks)	Number of patients (N)
Idiopathic	Active stimulation (cohort 1)	16
	Placebo (cohort 2)	16

Randomisation will be conducted using online randomisation software (www.randomiser.org). All participants will be blinded to the treatment being administered.

Prior to the treatment phase of the study, there will be a 4 week baseline phase to measure the rate of natural and spontaneous recovery. Outcome measures will be recorded at week 1 and week 4, and after the beginning of the treatment phase, every 4 weeks until the end of the study.

3. Outcome measures

The primary assessment time will be 12 weeks follow-up and the following outcome measures will be analysed:

- Non-motor symptom scale total score (NMSS)
- MDS-UPDRS 1 (Non-motor aspects of experiences of daily living)
- MDS-UPDRS 2 (Motor aspects of experiences of daily living)
- MDS-UPDRS 3 (Motor Examination)
- MDS-UPDRS 4 (Motor complications)
- MDS-UPDRS total score
- PD-39 total score
- Hospital Anxiety and Depression scale (HADS)
 - Depression total
 - Anxiety total
- Epworth sleepiness scale
- Fatigue severity scale
- Montreal Cognitive exam
- Timed up and go

4. Sample size

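### The planned EEG/ERP analysis compares alternating active and sham blocks that this parallel-group trial does not have, and the SAP puts nothing in its place

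*Protocol*

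**What the plan says.** Protocol 6.1 gives the only stated analysis of the electrophysiological measures: an ANOVA to "compare elements of the ERP and more global aspects of the EEG across alternating blocks of active and sham stimulation".

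The design is described differently elsewhere. SAP section 2 states: "This is a prospective single-blind randomised parallel group pilot study". Protocol 4.2 allocates participants 1:1. Cohort one (n=16) goes on to active stimulation, while cohort two (n=16) "will instead complete a placebo arm for the duration of the study protocol". Protocol 3.1 gives each arm a single type of session: the standard thermal waveform, or earpieces left without power.

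Protocol 6.1 also says that placebo patients may be offered active treatment after the study. They would then repeat their assessment schedule, "with the exception of EEG which given its time-consuming and burdensome nature will be dropped".

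On when EEG is recorded, the protocol has four statements:

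- Section 2.4: "Participants will undergo an EEG test at baseline and then at the end of the study protocol".
- Section 4.4: "EEG/ERP will be recorded at baseline and post-stimulation".
- Section 4.2, on the baseline assessment, which is described together with EEG/ERP: "This baseline will take place during the first week of enrolment and will then be repeated again during week 4".
- Section 4.2, directly after the sentence on four-weekly assessment: "Their physiological activity will also be measured using EEG and heart rate variability".

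The SAP does not mention EEG, ERP or heart rate variability.

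**The concern.** A comparison across alternating blocks is a within-participant contrast: each person must be recorded under both conditions. In a trial where each person receives only one, there are no data for it. The sentence therefore cannot be carried out, and the analyst would have to put something else in its place.

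Protocol 4.4 includes the electrophysiological markers to help explain mechanism and to give some objective support to assessments that are otherwise more subjective. The trial is single-blind, so that support has value. It is weakened if the contrast, the baseline and the time point are settled only once the data are in hand, particularly with several candidate measures (P300, alpha/theta index, power by frequency band) and several possible occasions. Protocol 6.1 itself acknowledges that EEG is a burden on participants, which is a further reason to have an analysis that can be run.

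**Working it through.** **Figures in the plan.** No sample size or precision figure is given for EEG, and Protocol 5.2 says that no formal calculation was done. The one figure that can be reproduced is recruitment: 32 / (1 − 0.20) = 40, as stated. The point does not depend on it.

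**Step 1: can the stated contrast be formed?** From Protocol 4.2 and the table in SAP section 2, 16 participants receive active stimulation only and 16 receive placebo only.

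- Participants in one condition only: 16 + 16 = 32.
- Participants with both: 32 − 32 = 0.
- The count stays at 0 if all 40 recruits are considered, since each is allocated to one arm.
- Protocol 3.1 places no sham period inside an active session and no active period inside a placebo session.
- The post-study offer is the only route to both conditions, and EEG is left out of it.

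**Step 2: does the SAP override the sentence?** The outcomes in SAP section 3 are NMSS (1), MDS-UPDRS parts 1 to 4 and total (5), PD-39 (1), HADS depression and anxiety (2), Epworth (1), fatigue severity (1), Montreal (1) and timed up and go (1). The count is 1 + 5 + 1 + 2 + 1 + 1 + 1 + 1 = 13, none electrophysiological. The ANCOVA in SAP section 6 is written for these outcomes and is not extended to EEG. Heart rate variability, recorded under Protocol 4.2 and 4.4, has no stated analysis in either document.

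**Step 3: which recordings would a corrected analysis use?**

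| Reading | EEG occasions | Per participant | For 32 |
|---|---|---|---|
| Protocol 2.4 | baseline; end of protocol | 2 | 2 × 32 = 64 |
| Protocol 4.4 | baseline; post-stimulation | 2 | 2 × 32 = 64 |
| Protocol 4.2, with Annex 1's follow-up visit taken to have no EEG | weeks 1, 4, 8, 12 | 4 | 4 × 32 = 128 |
| Protocol 4.2, full assessment repeated at follow-up | weeks 1, 4, 8, 12, 16 | 5 | 5 × 32 = 160 |

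The last two rows read the EEG sentence in 4.2 as carrying the four-week interval of the sentence before it. There may thus be one baseline recording or two. The end point in 2.4 may be week 12 (end of treatment in Annex 1) or week 16 (the maximum duration in Protocol 3.2).

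**Step 4: is the wording harmless?** As an illustration only, take equal SDs and one reading per condition, with the same correlation ρ between the two readings in either design. None of this is in the documents.

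- Within-participant contrast, n = 32: SE = SD × √(2(1 − ρ)/32).
- Baseline-adjusted ANCOVA, 16 v 16: SE = SD × √((1 − ρ²) × 2/16).
- Ratio of ANCOVA to within-participant SE = √(2(1 + ρ)).

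For ρ = 0.3 the SEs are 0.337 and 0.209 SD, ratio 1.61. For ρ = 0.9 they are 0.154 and 0.079 SD, ratio 1.95. The estimable contrast has a different error term and is less precise than the one described.

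**The case against.** The best reply is that the fault is two stray words. Without the reference to alternating blocks, Protocol 6.1 still names a method (ANOVA), broad measures and an active versus sham comparison, and 4.4 supplies markers and occasions. On that view an ordinary between-arm ANOVA is left, in a secondary mechanistic analysis of a pilot, and a minor correction would do. Part of this stands: the markers are named, and the clinical analyses are untouched. But even the repaired sentence would not say how baseline enters the model or which recordings count, and the sections disagree on the recordings.

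A second reply is that the four-week EEG interval is an inference. It is a reading, though the natural one, since the sentence says that EEG is also measured straight after stating the interval. The count of 5 is an upper limit: Annex 1 lists only a core assessment at follow-up. The schedule figures in Protocol 4.2 and 5.1 were not available in the text reviewed and might settle the timing. The written description of the arms is explicit without them.

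The description in Protocol 4.1 of a multiple single case approach could suggest alternation, but 3.1, 4.2 and SAP section 2 all describe fixed arms.

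A third reply is that a week 12 analysis presumes a week 12 recording, which might not exist if 2.4 means week 16. That is a fair reason to settle timing first. Protocol 4.4 (after stimulation) and 4.2 (full baseline assessment repeated at the end of treatment) both support a recording then. Lastly, ANCOVA is not the only cure: a between-arm ANOVA of change, or declaring EEG descriptive, would also remove the contradiction. ANCOVA is preferred because the SAP already uses it.

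**Conclusion.** The concern holds. The only stated EEG/ERP analysis rests on a contrast to which 0 of 32 participants can contribute, and neither the rest of the protocol nor the SAP replaces it. The conclusion follows from the written design and needs no outside figure; the precision ratios are illustrative and carry no weight in it. The range of 2 to 5 recordings per participant depends on how Protocol 4.2 is read, and shows how much is left open rather than any bias.

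The defect should be fixed, but it is limited to the mechanistic analysis. The 13 clinical outcomes and their ANCOVA are not affected.

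**What to change.** First, reconcile Protocol 2.4, 4.2, 4.4 and Annex 1 on when EEG is recorded: one or two baseline recordings, whether EEG is part of the four-weekly visits, and whether the final recording is at week 12, week 16 or both.

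Then replace the sentence in Protocol 6.1 with:

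> Each EEG/ERP measure (P300 amplitude, P300 latency, alpha/theta index and power in each main frequency band) at the end of treatment (week 12) will be compared between the active and placebo arms by ANCOVA with its baseline value as covariate. Baseline is the mean of the week 1 and week 4 recordings where both exist, and otherwise the single pre-treatment recording. The adjusted difference will be given with its 95% confidence interval. These outcomes are exploratory and mechanistic.

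Apply the same model to heart rate variability. If the reconciliation shows one baseline recording by design, drop the averaging. State in the amendment whether EEG data have already been examined by arm.

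The cost is one protocol sentence and, if wanted, a short SAP entry. No new data are needed, provided that the end-of-treatment recording described in Protocol 4.2 and 4.4 is made.

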3.2 Stopping criteria

We plan to administer multiple exposures to CVS in order to encourage experience-dependent long-term plastic change (Hoffman et al., 2002). We will study patients for a maximum of 16 weeks allowing for up to 8 weeks of stimulation. Our previous studies suggest that a 16 week protocol is likely to be feasible for patients and carers to commit to without becoming overly burdensome.

The trial will be stopped if the study clinicians (Drs [name]/[name]) and the chief investigator ([name]), or the local NHS R&D unit or sponsor, agree that a critical number of AEs have been reported. The trial may also be terminated if participants and their carers fail to comply with the stimulation protocol (2 x stimulation sessions per each day).

4. Study Design

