9.1 Analysis of Risk/ Benefit

We have previously conducted three NRES REC approved studies that have applied CVS (via the device described above) to neurological patients. Two of these studies have focused on patients with severe traumatic brain injury (in one study these patients were too disabled to self-consent): (i) Rec Ref: 14/EE/1041; An Initial Investigation into the Utility of Caloric Vestibular

Stimulation as a Treatment in Traumatic Brain Injury, and (ii) Rec Ref: 12/LO/0492 Does Vestibular Stimulation Aid Recovery From Low Awareness State? The third study (Rec Ref: 12/LO/1354 A non-invasive neuro-modulation device for migraine headache) focused on episodic migraine. All three studies utilized a similar treatment and assessment protocol to that proposed here and have not reported any serious events or reactions that could be associated with the study.

As noted previously, the aims of this Study involve the mitigation of neuropsychiatric symptoms in the PD subject population. Given the limited options available to the subjects who will be enrolled in the Study, improvement in their overall symptom burden will be viewed as significant. The CVS device is subject to the risks outlined below.

(1) Biocompatibility/toxicity

Biocompatibility is believed to be a minimal risk based on the selection and use of well-characterized materials. In addition, biocompatibility of the aluminum earpieces will be assessed in accordance with the requirements of ISO 10993.

(2) Infection control

Users are instructed to clean the device frequently (the earpieces and the surfaces touching the skin). The users are instructed to use 70% isopropyl alcohol wipes. This cleaning procedure will be independently validated.

(3) Side-effects

Adverse events associated with the application of CVS:

- The risk associated with the use of the CVS device is anticipated to be minimal (classified by the FDA for use in migraine as 'non-significant'). Mild nausea, dizziness and drowsiness are hallmarks of activation of the vestibular system, represent anticipated responses to this therapy and thus are not regarded as unanticipated side effects or AEs. The intensity of these symptoms is dose-dependent and reversible with discontinuation of the thermal stimulus. These symptoms typically resolve within 5-10 minutes after the discontinuation of stimulation.

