9.2 Monitoring of Research

The safety of this study will be regularly reviewed by the research team who will examine the specific study protocol, assess its risks and benefits, interpret the data, and assure that the study is conducted in the safest and most effective manner.

Although the proposed procedure is associated with minimal risk to subjects, the research team will regularly convene to monitor safety by reviewing AE reports and making future recommendations regarding appropriate safety procedures and proper use and interpretation of data to assure that subject participation is worthwhile.

9.2A Adverse Events

An AE includes any noxious, pathological or unintended change in neurological or bodily function as indicated by physical signs that occurs during the trial, regardless of whether it appears related or unrelated to the treatment.

All AEs will be graded for severity using the following criteria: Grade 0 = (none); Grade 1 = mild: No effect on activities of daily living; Grade 2 = moderate: partial limitation in activities of daily living; Grade 3 = severe: considerable limitation in activities of daily living—medical evaluation required. All AEs will be recorded by the patient and their carer/ care team on an individual diary card or directly to a member of the research team who will record the event using an AE form. A serious adverse event (SAE) is an AE that meets one of the following conditions: death, life-threatening situation (i.e. seizure), hospitalization, severe disruption of daily activity. If an SAE occurs during testing then immediate medical attention will be given from medical personnel at the on-site hospital facilities or by a qualified first-aider. Assessment and monitoring of AEs that occur between sessions will be based on verbal report by the patients and their carers. Patients and their carers will be given contact details so that they are able to report an AE to the research team at any time.

All AEs will be recorded using AE forms which will bear the subjects ID number and will remain on their secure electronic file visible to all members of the research team.

9.2B Discontinued Subjects

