Annex 1: Schedule of Events for idiopathic group

Enrolment/Screening	
 Informed Consent If enrolled, complete Screening Visit form If meet criteria complete participant questionnaire Arrange initial baseline assessment Arrange training session with CVS device
Days 1-4 (up to 4) in patient's home	
 Day 1/ 2- Device training session given to patient and their carer Day 3/4 - Administer full baseline assessment
Day 28: Subject repeats baseline	
 The full baseline assessment is repeated Subject performs a treatment under observation by a research team member to reconfirm proficiency
During the Treatment Period (weeks 4-12)	
 A research team member contacts the patient to ensure that she/he is using the Device consistently and making prompt diary entries A monthly assessment of the core symptoms of interest is completed at the patients' home
Final treatment visit for Subject	
 Complete full baseline assessment Patient returns CVS Device Collect all treatment delivery data from the CVS Device
Follow-up visit for Subject	
 Complete core assessment Debrief patient and carer Interview patient with regard to CVS Device

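### Adverse events are collected over the whole trial and summarised only by group, with no on-treatment window, although half of a completer's 16 weeks carries no stimulation

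*Protocol*

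**What the plan says.** Protocol 9.2A counts as an AE any qualifying change "that occurs during the trial, regardless of whether it appears related or unrelated to the treatment". Protocol 6.1 gives the only arm-level analysis: "Adverse events, general concerns, dropouts and satisfaction will be presented as summary statistics for each group". Section 9.2A also grades severity, and 9.2C promises tables of AE frequency by category, but neither mentions study phase. The SAP contains no AE analysis.

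The schedule has three parts:

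- **Before treatment.** Protocol 2.4: "Participants will first complete an initial 4 week period of baseline assessment".
- **Treatment.** Annex 1 places the treatment period in weeks 4-12.
- **After treatment.** Protocol 4.2: "4 weeks post-intervention, the full baseline assessment will once again be repeated to assess carryover".

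Protocol 3.2 gives the total: "We will study patients for a maximum of 16 weeks allowing for up to 8 weeks of stimulation". Under 4.2, allocation takes place at registration, so events in the baseline phase already belong to an arm.

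**The concern.** Followed as written, 6.1 and 9.2A lead to one whole-trial AE summary per arm. The device can cause a difference between arms only during or after stimulation, yet the summary also takes in the four weeks before stimulation starts and the four weeks after it ends. Background events from those weeks enter both arms and pull relative measures towards no difference, which is the direction that favours the device.

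The plan does take account of phase for efficacy: the SAP averages the week 1 and week 4 baselines and fixes 12 weeks as the primary time. Safety has no counterpart. The study is a pilot meant to inform a larger trial, and an AE rate during stimulation is one of the things that trial's designers would want from it.

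Exposure will also vary between participants. The SAP expects 20% dropout by 12 weeks, and protocol 9.2B replaces discontinued participants, but no exposure denominator is planned.

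**Working it through.** **The plan's own figure.** 4 weeks (2.4) + 8 weeks (Annex 1, weeks 4-12) + 4 weeks (4.2) = 16 weeks, which agrees with 3.2. The unstimulated share is 8/16 = 50% for a participant who completes everything.

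**Model.** The documents give no AE rate, so the following are assumptions. Let b be the background AE rate per participant-week, the same in both arms and all phases. Let R multiply that rate in the active arm during the 8 stimulated weeks only. Counts are Poisson with 16 per arm (SAP section 2).

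**Rate ratio.** Treatment phase: 8bR / 8b = R. Whole trial: (8bR + 8b) / 16b = (1+R)/2. This does not depend on b.

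| True R | Whole-trial ratio |
|---|---|
| 2 | 1.5 |
| 3 | 2.0 |
| 4 | 2.5 |

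**Worked case, b = 0.05 and R = 3.**

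- Expected events, treatment phase: 16 × 8 × 0.05 × 3 = 19.2 active; 16 × 8 × 0.05 = 6.4 placebo.
- Expected events, whole trial: 19.2 + 6.4 = 25.6 active; 16 × 16 × 0.05 = 12.8 placebo.
- Difference in events: 19.2 − 6.4 = 12.8 and 25.6 − 12.8 = 12.8. Both are 12.8/16 = 0.80 per participant, so the count difference is unchanged.
- Standard error of that difference: √(19.2 + 6.4) = 5.06, against √(25.6 + 12.8) = 6.20. The same difference is noisier.
- Excess per participant-week: 0.80/8 = 0.100, against 0.80/16 = 0.050.
- Participants with at least one AE, treatment phase: 1 − e^(−1.2) = 70% against 1 − e^(−0.4) = 33%, a difference of 37 points.
- Participants with at least one AE, whole trial: 1 − e^(−1.6) = 80% against 1 − e^(−0.8) = 55%, a difference of 25 points.

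**Range.** For b from 0.02 to 0.10 and R from 2 to 4, the fall in that risk difference runs from 13 to 11 points (b = 0.02, R = 2) up to 41 to 18 points (b = 0.10, R = 4). No AE test is planned, so power is only a yardstick. With an exact two-sided 5% comparison of counts, the whole-trial window loses between about 0 and 18 percentage points of power over this range; in the worked case power falls from 0.66 to 0.48.

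**Sensitivity to reporting.** If only a fraction c of background events is captured in the unstimulated weeks, the whole-trial ratio is (8R + 8c)/(8 + 8c) = (R + c)/(1 + c). With c = 0.5, R = 2 gives 2.5/1.5 = 1.67 and R = 3 gives 3.5/1.5 = 2.33. Weaker reporting off treatment therefore makes the dilution smaller.

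**The case against.** The strongest reply is that 9.2A says what is collected, that 6.1 is a single sentence with no stated window, and that collecting every event regardless of relatedness is good practice. The study is a descriptive pilot, and a later split might be possible because the device logs its sessions (protocol section 3). This stands in part. Pooling is the default reading and is not an explicit instruction. But no section says that AE onset dates are recorded, and no split is planned.

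A reader might also infer four stronger points, which the documents do not support:

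- **Half of the excess harm disappears.** This is true of the weekly rate but not of the counts, where the difference between arms is identical in both windows.
- **The claimed reversibility cannot be shown because phases are pooled.** Section 9.1 says "The intensity of these symptoms is dose-dependent and reversible with discontinuation of the thermal stimulus", but this refers to mild nausea, dizziness and drowsiness, which the same paragraph does not regard as AEs and expects to resolve in 5-10 minutes. Ear canal irritation is expected to resolve within hours. A table by phase could test neither; it could show only whether AEs persist after week 12.
- **The stopping decision is weakened.** Section 3.2 refers to a critical number of AEs. That is a count, and extra weeks cannot dilute a count.
- **Collection outside weeks 4-12 depends on visits alone.** Annex 1 lists contact about "making prompt diary entries" only in the treatment row, but 9.2A lets participants report at any time. Prompting is uneven on paper; reporting is not closed off.

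One further caution is fair. The trial looks for durable effects and carryover, so the treatment phase should not be the only window shown.

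**Conclusion.** The point holds as a gap in the AE analysis plan with a definite direction. With 8 of a completer's 16 weeks unstimulated, a whole-trial rate ratio shrinks from R to (1+R)/2, and weekly rates and the proportion with any AE move towards no difference. Absolute count differences keep their size and lose precision. The pilot has no planned on-treatment AE rate to pass on.

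The size rests on a constant background rate, equal reporting in all phases, full 16-week follow-up, and an effect confined to the stimulated weeks. It would be smaller if off-treatment reporting is weaker or if harms continue after week 12. Eight weeks of stimulation is a maximum, so shorter treatment with full follow-up would increase the dilution. The boundary is also not perfectly clean, because Annex 1 places device training on days 1-2 and an observed treatment on day 28. Since AE reporting is descriptive, this is a reporting weakness worth correcting and does not threaten the trial's validity.

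**What to change.** Amend protocol 6.1 and 9.2C, and add an AE section to the SAP:

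1. Record onset and resolution dates for every AE and SAE.
2. Tabulate events, participants with an event, and exposure time by arm for four periods: pre-treatment; treatment (weeks 4-12, bounded by the first and last sessions in the device log); post-treatment follow-up; and any later active treatment of placebo participants offered under 6.1. Without the last category, a table by randomised group could place active exposure in the placebo arm.
3. Make the treatment phase the main descriptive safety comparison, and show whole-trial totals beside it.
4. State explicitly which period takes events arising from the training session and from the observed day-28 treatment.
5. Use the same AE enquiry and diary prompting in every phase.

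The cost is wording, a few more table columns, and diary use extended over the roughly 8 weeks outside the treatment period. No new visits are needed.
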